3.5 Framework

Superiority of both proteomic test (CKD273) and active comparator.

3.6 Interim analysis/ Stop rules

No statistical interim analysis was planned or conducted. An independent safety monitoring committee conducted annual safety analysis in case of unbalanced SAE/death between placebo and comparator allocation. In total, four planned and no unscheduled DMC reviews were conducted and no unbalance or concern was identified.

3.7 Timing of final analysis

The final analysis will be performed after data-lock. Data lock will be permed by Data management at Hannover Clinical Trial Center, holder and responsible for eCRF. Data lock will be done after written confirmation from the sponsor and after entry of all available data.

4 STATISTICAL PRINCIPALS

4.1 Confidence limits and significance level

Any p-value below 0.05 will be considered statistically significant. A p-value will be calculated for the primary analysis. P-values for the secondary analyses will only be calculated if the primary analysis yields a p-value below 0.05. For all primary and secondary analyses 95 % confidence limits will be calculated.

Continuous values fulfilling terms of normal distribution will be displayed as mean values and 95 % confidence limits of the mean. Variables not fulfilling terms of normal distribution will be displayed as median and inter quartile range from p25 to p75.

4.2 Adherence and protocol deviations

The study is conducted in accordance with GCP and monitoring. All minor protocol deviations are recorded in the eCRF. All major protocol deviations were brought to the attention of the sponsor, recorded in the eCRF and site-specific trial master file.

4.3 Analysis populations

4.3.1 Screening population

All participants with a valid informed consent and data entry at the screening visit.

4.3.2 Observational cohort

All participants with valid proteomic score and data at baseline visit.

4.3.3 Intention to treat cohort

All participants with a valid proteomic score with a high-risk pattern who was provided with study medication

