	
The expected relative proportions of diabetes type 2 patients developing microalbuminuria in our study population are: 24% in patients at high-risk for diabetic nephropathy in the treatment group, 40% in those patients at high-risk for diabetic nephropathy in the placebo group and 8.5% in those therapy-naive patients at low-risk for diabetic nephropathy. Using the samples size formula for two proportions test (<math>\alpha=0.05</math> <math>\beta=0.80</math>), randomized (1:1), <math>n=129</math> in each arm of the intervention group. To account for drop-outs we plan to randomize 300 in all. It is expected that approx. 15% of the population will show a pattern of high-risk of CKD, therefore 2000 patients have to be included. Equal drop-out frequency is expected in both groups and there will be no replacement of drop-out. Discontinuation prior randomization is categorized screening failure.
 
Analysis populations: The primary analysis will be conducted for all patients included (intent-to-treat population) in the observational and intervention study groups. In addition, all relevant efficacy endpoints will be also analyzed for the per protocol population in both study groups.
 
Analysis of primary endpoint: Cox regression analysis of development of the primary endpoint adjusted for age, gender, study site will be conducted in both study groups (observational and intervention) and for study intervention in the interventional group. Secondly adjusted in addition for baseline UACR, HbA1c and BP.
 
Analysis of secondary endpoints: Cox regression analysis of development of secondary endpoints in the both study groups (observational and intervention) as well within the interventional group (high- vs. low-risk), adjusted for age, gender, study site and study intervention with secondary adjustment for baseline UACR, HbA1c and BP.
 
Assessment of safety: The assessment of safety will be based primarily on the frequency of eCRF-documented AEs, laboratory abnormalities, and SAEs (see section 13.3). Occurrence and frequency of eCRF-documented AEs, SAEs and laboratory abnormalities will be summarized by treatment group.
 
In addition AEs leading to death and AEs leading to discontinuation of study medication and/or withdrawal will be summarized for the two treatment groups.
 
Final analysis plan: Statistical analysis of the data will be performed by Steno Diabetes Center. A statistical analysis plan will be written and signed before database lock and unblinding of the entire treatment code.
 
Methods for imputation and type of censoring will be clarified in the statistical analysis plan prior to database lock and unblinding.

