## **10.6 Dispensing of investigational medicinal products**

Study medication will be provided to the patients of the high-risk population at baseline and at each study visit. Prior to receiving the IMP patients will be informed orally and in writing of the contents of the IMP as describes in section 11.1 and the potential side effect described in section 11.3.

At every visit after baseline (every 13 week) patients has to return the unused IMP for accountability and destruction of unused tablets according to section 11.2.

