## **10.12 Randomization**

Randomization will be performed at the baseline visit. If the patient participates in the biobank the randomization will be performed after collection of samples. Only patients with a high-risk pattern in the proteomic analysis from the screening visit will be randomized. Patients will be randomized in a 1:1 ratio to either active medication or placebo in addition to standard treatment as described in section 8. Patients will be stratified in the two treatment arms (1:1) based on whether or not the patients is treated with RAS blocking agents at the time of entry (Screening).

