### 11.2 Accountability procedures for the IMP

After randomization, patients of the intervention group will receive IMP from the study site they attend.

At every 13th week after the Baseline the patients should be asked to return the IMP for accountability.

Patient should take between 80-110% of IMP to be compliant. The process for capturing the compliance information is the assessment by tablet counts at each site.

A record of all IMP movements including drug dispenses must be performed and documented by each site.

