## 15.5 Final analysis plan

Statistical analysis of the data will be performed by Steno Diabetes Center. A SAP will be written and signed before database lock and unblinding of the entire treatment code. Methods for imputation and type of censoring will be clarified in the SAP.

The primary efficacy analysis will be performed for all patients randomized, which is the intent-to-treat population. In addition, the primary and secondary efficacy endpoints will also be analyzed for the per-protocol population. The per-protocol analysis population includes all patients who were randomized into the double-blind study received study medication for at least 3 days.

For all analyses a p value <0.05 is considered significant.

Tables will be created for baseline variables, and comparisons performed between low- and high-risk population, and in the intervention group for active vs. placebo treatment. Furthermore, tables with observations from study visits will be provided for the observational part and for the intervention study.

Analyses not described here or in the SAP will be considered exploratory/post hoc analyses.

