6.3.2 Intervention study (Intention to treat cohort)

6.3.2.1 Primary analysis of primary endpoint

In the intention to treat cohort, a comparison between active and placebo treatment will be performed in a Cox-regression model including data on the primary outcome. Adjustments in the model will only be performed for eGFR and/or UACR in the case of a significant unbalance in the baseline value (significance level for unbalance between treatment allocation groups is a p-value < 0.01).

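### The SAP's intention-to-treat cohort is limited to high-risk patients provided with study medication, whereas protocol 15.5 takes all randomised patients, so the primary randomised comparison can lose patients after allocation

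*SAP*

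**What the plan says.** Three texts define the intention-to-treat population, and they differ.

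- Protocol 15.5: "The primary efficacy analysis will be performed for all patients randomized, which is the intent-to-treat population".
- Protocol synopsis: "The primary analysis will be conducted for all patients included (intent-to-treat population) in the observational and intervention study groups". This covers both parts of the study and is not tied to randomisation.
- SAP 4.3.3: "All participants with a valid proteomic score with a high-risk pattern who was provided with study medication".

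The SAP's set governs the key randomised comparison. SAP 6.3.2.1 states: "In the intention to treat cohort, a comparison between active and placebo treatment will be performed in a Cox-regression model". The per-protocol cohort in SAP 4.3.4 is a subset of it. Neither the sensitivity analyses (SAP 6.3.2.3) nor the additional analyses (SAP 6.4) include one of all randomised patients.

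On the order of events, protocol 10.12 says "Randomization will be performed at the baseline visit", protocol 11.2 says "After randomization, patients of the intervention group will receive IMP from the study site they attend", and protocol 10.6 says "Study medication will be provided to the patients of the high-risk population at baseline and at each study visit".

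**The concern.** Under the SAP, a patient's place in the primary comparison depends on a step that comes after allocation. That makes the set a modified intention-to-treat population under an intention-to-treat label. Someone reading the report would assume that every randomised patient is counted.

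The change was not among the matters that protocol 15.5 expressly handed to the SAP, which concern imputation and censoring: "Methods for imputation and type of censoring will be clarified in the SAP". The SAP gives no reason for the narrower set and does not ask for exclusions to be counted by arm. It also fits poorly with protocol 14.6 and 24.5, which keep patients under observation after they stop study medication so that endpoints are captured as fully as possible.

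At stake is whether the arms being compared are exactly those that randomisation produced. If the excluded patients differed between arms in their risk, the hazard ratio would shift for reasons unrelated to treatment.

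**Working it through.** **1. Who is in one population and not the other**

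| Patient | Protocol 15.5 | SAP 4.3.3 |
|---|---|---|
| Randomised, dispensed, score valid and high-risk | In | In |
| Randomised, dispensed, never takes a tablet or stops early | In | In |
| Randomised, no pack dispensed | In | Out |
| Randomised, score later judged invalid or not high-risk | In | Out |

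The last two rows are the whole difference. The last assumes that a score could be re-judged after randomisation; the documents describe no such process.

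**2. The plan's own sample size**

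Inputs (SAP 3.4): 40% placebo, 24% active, 1:1 allocation, 80% power (printed as beta), alpha 0.05, taken as two-sided in line with protocol 15.6. With unpooled variance:

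n = (0.40×0.60 + 0.24×0.76) × (1.960 + 0.842)² / 0.16² = 129.5 per arm

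The plan states 129; strict rounding up gives 130. For 258 patients and 10% drop-out, 258 / 0.90 = 286.7, so 287. The planned 300 covers that.

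**3. Power if patients are dropped**

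The documents do not say how many randomised patients go undispensed, so the loss k per arm is an assumption. With n = 150(1 − k) per arm and mean proportion 0.32:

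power = Φ{[0.16 − 1.960 × √(2×0.32×0.68/n)] / √(0.4224/n)}

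At n = 150 this is Φ[(0.16 − 0.1056) / 0.0531] = 84.7%.

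The third column below keeps all 150 per arm but assumes that undispensed active-arm patients have the placebo risk, so the active proportion is 0.24(1 − k) + 0.40k.

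| k (assumed) | Undispensed dropped | All randomised kept |
|---|---|---|
| 0 | 84.7% | 84.7% |
| 1% | 84.4% | 84.0% |
| 2% | 84.0% | 83.2% |
| 5% | 82.9% | 80.6% |
| 10% | 80.8% | 76.0% |

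At 1% to 2%, the choice moves power by less than one percentage point either way.

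**4. Outer bound on bias**

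Suppose there is no true effect (40% in both arms, 60 events in 150) and the only patients excluded are m active-arm patients who would have had the event. The active proportion becomes (60 − m)/(150 − m), and the approximate hazard ratio is ln(1 − p)/ln(0.60).

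| m | Active proportion | Apparent hazard ratio |
|---|---|---|
| 1 | 59/149 = 39.6% | 0.99 |
| 3 | 57/147 = 38.8% | 0.96 |
| 5 | 55/145 = 37.9% | 0.93 |

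This needs every exclusion to fall in one arm and on future events. It is a limit, not a forecast.

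**The case against.** The strongest reply is that the two populations will nearly coincide.

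- The condition is provision, not use. Non-adherent patients stay in, and under SAP 5.4 withdrawn patients contribute time up to their last observation.
- Randomisation and first dispensing are at the same baseline visit.
- Active and placebo packs are indistinguishable (protocol 8.4 and 11.1, SAP 3.3). A patient not handed a pack is lost before any exposure and normally before anyone could know the arm, so there is no evident route to arm-related selection.
- The SAP's silence on randomisation matters little, because only the intervention group receives study medication (protocol 11.1), and only after randomisation. SAP 6.3.2.1 and 6.3.2.2 also refer to treatment allocation, which points to analysis by assigned arm.

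All of this stands, and it limits the size of the problem. It does not reconcile the definitions or supply the missing analysis of all randomised patients.

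Three stronger readings are tempting. A reader might infer that the randomised comparison is compromised; the blinded, same-visit dispensing gives no support for that. A reader might infer that a registered population was abandoned; the documents show only a departure from the protocol. A reader might infer that the dispensed set should become the safety set. The protocol, however, starts adverse event documentation at first administration (13.3.1.1) and summarises laboratory grades after the first dose (15.8), and neither is the same as dispensing.

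**Conclusion.** The point holds as a conflict between the SAP and the protocol over the primary randomised population. SAP 4.3.3 as written permits exclusions after randomisation from an analysis called intention-to-treat, and SAP 6.3.2.1 relies on it.

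The expected effect is small. Each 1% undispensed is 3 of 300 patients. An assumed equal loss of 1% to 10% per arm leaves power between 84.4% and 80.8%, against 84.7% with no loss. A material bias would need exclusions concentrated in one arm and related to outcome, which the design makes unlikely. These figures rest on the plan's 40% and 24% event proportions and on assumed losses; the true count is not in the documents.

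It should still be corrected. If no one is excluded, the correction changes no result; if someone is, it restores the comparison the protocol specified.

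**What to change.** Change SAP 4.3.3 to all randomised patients, analysed in the arm assigned, whether or not study medication was provided and whatever later becomes of the score. Report by arm the number randomised but not dispensed, with reasons. Bring the synopsis wording into line with protocol 15.5.

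If the sponsor wishes to keep the dispensed set for efficacy, label it modified intention-to-treat and use it only as a supportive analysis beside the all-randomised one.

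The cost is one sentence in the SAP, one line in the disposition table and a wording alignment in the synopsis. Two dependent places need a check: the per-protocol cohort in SAP 4.3.4, which is built on 4.3.3, and the safety tests in SAP 6.3.2.2, which sit under the same cohort heading. No new data are needed. The change should be made before the SAP is finalised and the treatment code is opened (protocol 8.5.2 and 15.5).

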4.3.4 Per protocol cohort

All include in the intention to treat cohort AND with an accountability between 80 % and 110 % at more than 95 % of the study period

5 TRIAL POPULATION

5.1 Screening data

Patients who discontinue prior randomization for any reason are considered screening failures.

If a patient are considered a screening failure, demographic information (sex, age, onset of diabetes and race) are to be documented, as well as primary reason for discontinuation.

5.2 Eligibility

All participants who fulfil all inclusion and no exclusion criteria and with a valid signed informed consent were eligible.

Summary of inclusion criteria:

- Age 18 to 75, Type 2 diabetes,
- Persistent normoalbuminuria (at least 2 of 3 UACR < 30 mg/g)
- eGFR > 45 ml/ min/ 1.73 m²
- Not pregnant or intent to become pregnant in the trial period

Summary of exclusion criteria:

- Uncontrolled hypertension
- Type 1 diabetes
- Current in dual blockade with both ACE and/or ARB and/or direct renin inhibition
- Current use of MRA
- Hyperkalemia: Plasma potassium level >5.0 mmol/L or serum potassium level >5.4 mmol/L.
- Current cancer treatment or within five years
- Diagnosis of non-Diabetic CKD current or in the past
- Known or suspected abuse of alcohol or narcotics
- Participation in any other intervention trial than PRIORITY

5.3 Recruitment

5.3.1 Recruitment period

Recruitment started in March 2014. The recruitment period will run from approval by REC and NCA in the participating countries and until the 31st of August 2016.

5.3.2 Patients

It is intended to observe/ treat each patient for at least two years after baseline. Patients included prior to October 2016 will be observed/ treated for more than two years depending on the time of inclusion. The observation/ treatment period can't exceed 4.4 years. All patients will have final assessment performed in the period from 1st July 2018 to 15th October 2018.

5.3.3 Site

15 sites in 10 countries were active recruiting.

5.4 Withdrawal/ follow-up

Time of follow-up will be estimate from baseline to end – exposure time measure in day/years. Participants who withdraw will be included in the analysis with exposure time from baseline to last observation. Participants who withdraw consent are included in the statistical analysis unless they specifically also withdrawal consent to use of data already entered in the eCRF.

5.5 Base characteristics / data description

Variable (reporting methods, [unit])

- Gender (N, % male)
- Medical history
 - o Diabetes duration (mean, SD, [years])
 - o Cardiovascular disease, hypertension, dyslipidemia [%]
 - o Retinopathy/ maculopathy (grade, [%])
 - o Smoking (grade, [%])
- Concomitant medication
 - o Use of antidiabetic medication (active substance group, [%])
 - o Use of antihypertensive agents (active substance group, [%]).
- Vital signs
 - o Systolic and diastolic blood pressure (Mean, SD, [mmHg]).
- Blood sample
 - o Creatinine, sodium, and potassium, HbA_{1c}, cholesterol, HDL, LDL, and triglycerides. (mean, SD)
- Urine sample
 - o Proteomic score (CKD273) (high, low-risk) (N, mean, [%])
 - o Urine albumin to creatinine level. (median, IQR, [mg/g])

6 ANALYSIS

6.1 Outcome definition

6.1.1 Primary outcome

Development of confirmed microalbuminuria (UACR >30 mg/g) in at least two out of three first morning voids with $\geq 30\%$ increase (geometric mean) in UACR from “run-in” period samples OR > 40 mg/g (geometric mean).

6.1.2 Secondary outcome

- A. Comparison of composite fatal and non-fatal cardiovascular outcome (MI, stroke, CABG, PTCA, hospitalization for heart failure and CVD) and all-cause mortality during the study.
- B. Comparison of incidence of retinopathy and frequency of laser treatment. Data collected from self-reported AEs.
- C. In addition to the categorical analysis of UACR, an analysis will be performed with changes in geometric mean of UACR throughout the study period in all patients by assessing the slope of albuminuria changes and absolute changes from inclusion to end of trial.
- D. Development of microalbuminuria (UACR >30 mg/g) in at least one morning void urine sample will be used as a secondary outcome instead of confirmed microalbuminuria.
- E. Development of macroalbuminuria (UACR >300 mg/g) in 2 out 3 first morning void urine samples).
- F. For patients with eGFR ≥ 60 ml/ min/ 1.73 m² at baseline, development of eGFR <60 ml/min/1.73m².
- G. Development of CKD stage 4 (eGFR <30 ml/min/1.73m²).
- H. Change in eGFR (slope) from baseline and from three-month post-baseline to end of study.
- I. Change in eGFR (40 % reduction) from baseline and from three-month post-baseline to end of study.
- J. Safety: Adverse Events and Serious Adverse Events. Adverse Events leading to death or discontinuation of study medication and/or withdrawal.
- K. Event of hyperkalaemia with potassium level in plasma ≥ 5.5 mmol and/or ≥ 5.8 mmol in serum at any time point.

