### 5.5 Secondary endpoints

#### 5.5.1 In the total population:

In the following paragraphs patients in the intervention group, (group B) and observation group (group A) will be compared.

- Comparison of composite fatal and non-fatal cardiovascular outcome (MI, stroke, CABG, PTCA, hospitalization for heart failure and CVD), and all-cause mortality during the study.

- Comparison of incidence of retinopathy and frequency of laser treatment. Data collected from self-reported AEs
- In addition to the categorical analysis of urinary albumin excretion, an analysis will be performed with changes in geometric mean albuminuria throughout the study period in all patients by assessing the slope of albuminuria changes and absolute changes from inclusion to end of trial
- Development of microalbuminuria (UACR >30 mg/g) in at least one morning void urine sample will be used as a secondary outcome instead of confirmed microalbuminuria
- Development of macroalbuminuria (UACR >300 mg/g in 2 out 3 first morning void urine samples)
- For patients with eGFR  $\geq 60$  at baseline, development of eGFR <60 ml/min/1.73m^2.
- Change in eGFR (slope and absolute from baseline and from 3 month post-baseline to end of study)

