## 6.2 Observation group (group A) / Low-risk population

It is expected that 85% of the total population (approx. 1700 patients) will show a low-risk pattern. Patients should be followed by the investigator in routine clinics or seen once yearly, for standard diabetes care according to local guidelines. Annual measurements of UACR, BP, medication, and locally measured creatinine, sodium, potassium, and lipids (cholesterol, HDL, LDL, triglycerides) will be performed. HbA1c will be measured in DCCT-aligned quality control programs or IFCC. During the study, the medical history regarding vascular events, current retinopathy status (by history) and information on laser treatment, as well significant medical events (see section 10.14.), including hospital admissions, are registered.

Secondary endpoints and significant medical events will be registered at the annual visits.

After the last study visit, patients will continue in the observational long-term follow-up in accordance with section 6.4.

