## **10.14 Significant medical event**

Documentation of significant medical events will be conducted at the annual visit for the low-risk participants. Any medical untoward occurrence after baseline can be documented as a significant medical event. Of special interest are events described in section 5.5.1 as secondary end points.

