## 11 INVESTIGAL MEDICAL PRODUCTS

### 11.1 IMPS

All IMPs will be manufactured in accordance with EU Good Manufacturing Practice requirements and will be supplied and distributed by Mawdsleys Clinical Services UK.

Tablets and bottles containing active IMP or placebo will be indistinguishable from each other in terms of taste, appearance, durability, packaging, labeling and instruction for use.

Only patients of the intervention group will receive IMP. Only those supplies intended for use in the study may be dispensed to study participants.

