## **13.3 Documentation and reporting of AE**

### **13.3.1 Documentation requirements**

#### **13.3.1.1 AEs**

AE will be collected by the investigator either based on the information provided spontaneously by the patient or evaluated by non-suggestive questions.

The following information is necessary:

- Type of AE (disease, symptoms)
- Classification (serious vs. nonserious)
- Start and termination date of the AE
- Grading of AE-intensity (grade 1-5). The descriptions and grading scales found in the revised NCI CTCAE version 4.0 will be used for adverse event reporting.
- Causality to the study drug
- Measures taken with regard to study medication and treatment of the AE
- Outcome of the AE

The AE documentation period for this trial begins upon first administration of the IMP. In case of continuation of any AE the documentation period will be prolonged until all AEs are resolved or until the investigator assesses the adverse events as "chronic" or "stable".

Site investigator is responsible for monitoring the safety of patients enrolled into the study at the study sites. All AEs will be documented in the patient's medical record and managed according to standard practice.

The following AEs will additionally be documented in the eCRF:

- AEs leading to study drug discontinuation and/or withdrawal
- Serious AEs (SAEs, see Section 13.1.3)
- AEs related to cardiovascular and/or renal disease
- AEs related to retinopathy (and corresponding laser treatment)

- Laboratory abnormalities suspected by the investigators to be related to the study drug including the potassium and sodium value

At each patient visit the investigator will review the patient's medical record and determine if there have been any serious adverse events (SAEs) and/or AEs to be documented.

All eCRF-documented AEs, SAEs and laboratory abnormalities must be graded for severity and relationship to study drug and will be coded using the MedDRA via MARVIN.

Documentation of AEs must be performed in a timely manner on the respective AE forms in the eCRF.

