6.3.1.2 Analysis of secondary endpoints

Based on a 2x2 table included the primary endpoint (event/ event free) vs. risk stratification ("high"/- "low"-risk) we will calculate sensitivity, specificity and numbers need to screen for CKD273 and tested for significance using Chi-square test. In a logistic model we will added value using AUC and ROC with comparison between "high"- and "low"-risk vs. event and event-free for both primary endpoint. The logistic models will be performed both unadjusted and adjusted for age, gender, HbA_{1c}, systolic blood pressure, retinopathy, eGFR and UACR at baseline.

For the Cox-regression model a model, including adjustment for age, gender, Hba1c, systolic blood pressure, retinopathy eGFR and UACR at baseline will be comprised for secondary endpoints (see section 6.1.1 and 6.1.2, excluding 6.1.2 C, H and J).

For further clarification of the added value for discrimination, the rIDI will be calculated based on all above described Cox-regressions models with a significant HR for CKD273 in the unadjusted model for each endpoint.

To evaluate changes in UACR and eGFR over time (outcome measurement C and H in section 6.2.1) a linear mix model will be applied with adjustment for eGFR and UACR at baseline.

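### SAP outcome B (retinopathy and laser) names adverse events as its only source, but low-risk patients are recorded on a different, annual form that the SAP never mentions

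*SAP*

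**What the plan says.** SAP 6.1.2, outcome B, gives both the outcome and its source: "Comparison of incidence of retinopathy and frequency of laser treatment. Data collected from self-reported AEs". Protocol 5.5.1 uses the same source, under an introduction that sets the contrast: "In the following paragraphs patients in the intervention group, (group B) and observation group (group A) will be compared".

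SAP 6.3.1.2 fits adjusted Cox models for high versus low risk to the outcomes listed as "see section 6.1.1 and 6.1.2, excluding 6.1.2 C, H and J". B is not among the exclusions, so it is analysed.

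On adverse events, Protocol 13.3.1.1 says: "The AE documentation period for this trial begins upon first administration of the IMP". Protocol 11.1 says: "Only patients of the intervention group will receive IMP". For these patients the eCRF has a dedicated category, "AEs related to retinopathy (and corresponding laser treatment").

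Low-risk patients have a different record. Protocol 10.14 says: "Documentation of significant medical events will be conducted at the annual visit for the low-risk participants". Protocol 6.2 adds that "current retinopathy status (by history) and information on laser treatment" are registered for them, and that secondary endpoints are registered annually. Protocol 6.3 describes the same by-history information for the intervention group, in addition to adverse events, with visits every 13 weeks.

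**The concern.** The named source belongs to one side of the comparison. An analyst who takes SAP 6.1.2 and 6.3.1.2 at their word would search the adverse event data and find no low-risk patients there. An analyst who sees the problem would have to choose a substitute at analysis, with no rule in the SAP for which form, which terms or which dates to use.

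Both routes favour finding more, or earlier, events in the high-risk stratum. If the primary analysis is significant, SAP 4.1 allows p-values for secondary outcomes. A significant unadjusted hazard ratio for CKD273 then triggers an rIDI calculation under SAP 6.3.1.2. A difference produced by how events were recorded could therefore be reported as added value of the proteomic test.

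**Working it through.** The plan states no figure for this outcome, so there is none to reproduce. The check is a trace of the text, a count of visits, and an illustration under stated assumptions.

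**1. From outcome to data**

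| Step | High risk (group B) | Low risk (group A) |
|---|---|---|
| Receives study drug (Protocol 11.1) | yes | no |
| Adverse event recording (Protocol 13.3.1.1, Table 1) | yes, from first dose | not scheduled |
| Significant medical event recording (Protocol 10.14, Table 1) | not scheduled | annual and final visit |
| Retinopathy and laser by history (Protocol 6.2, 6.3) | described | described |
| Source named in SAP 6.1.2 B | adverse events | adverse events |

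The last row does not fit the low-risk column. The SAP does not mention significant medical events or the by-history record as sources for this outcome.

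**2. Scheduled recordings in Table 1**

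- Group B, adverse events: week 2 (1) + weeks 13 to 221 in steps of 13 (17) + final visit (1) = 19 at most.
- Group A, significant medical events: weeks 52, 104, 156 and 208 (4) + final visit (1) = 5 at most.
- By week 104, the minimum intended follow-up: group B has week 2 + eight 13-weekly visits = 9; group A has 2. The final visit adds one to each if it is separate.

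The maxima apply to the earliest recruits. Under Protocol 14.6, patients who stop study drug move to the observational visit schedule, so some group B patients have fewer.

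**3. Illustration**

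Inputs: the planned split of 300 high-risk and 1700 low-risk patients (Protocol 6.1). The SAP gives a cohort of 1811 without its split. The documents give no retinopathy rate and no capture rate. Assume the same true incidence *p* in both strata, from 1% to 10%, full capture in group B, and capture of a fraction *c* in group A.

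Observed risk ratio = (300*p*/300) ÷ (1700*pc*/1700) = 1/*c*.

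- *c* = 0 (adverse event forms only): 300 × 0.01 = 3 events against 0 (Fisher exact p = 0.003), up to 300 × 0.10 = 30 against 0 (p < 0.0001). The hazard ratio cannot be estimated.
- *c* = 0.5: 1/0.5 = 2.0 (2.0 to 2.1 with events rounded to whole numbers).
- *c* = 0.8: 1/0.8 = 1.25 (1.2 to 1.3 with rounding).
- *c* = 1: risk ratio 1.0.

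The direction follows from the design. The size depends entirely on *c*, which is unknown.

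**4. Existing protection**

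SAP 6.3.1.3 recognises the unequal visit frequency and moves high-risk events to the next annual visit, but for the primary endpoint only. SAP 6.4 adds a model restricted to annual samples for high-risk placebo versus low-risk patients. It names no outcome, and the reference to samples points to UACR. Neither rule reaches outcome B.

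**The case against.** A reader might infer that the comparison is wrong by construction because low-risk patients have no record of retinopathy or laser treatment. The documents do not support that. Protocol 6.2 registers this information and the secondary endpoints for them each year, and Protocol 10.14 directs significant medical events at the secondary endpoints of section 5.5.1, which include this one.

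The protocol also uses the term adverse event loosely. The definition in 13.1.1 runs from baseline, not from first dose. Section 10.4 asks for new examination findings to be recorded as adverse events, although both groups are examined. On that view the outcome's source could be meant to include the significant medical event form. This is a fair reading of intent. It does not settle the matter, because 13.3.1.1 and Table 1 tie the formal record to group B and the SAP says nothing further.

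It can also be said that an annual question may recover the whole preceding year, so that less frequent asking mainly affects dates and recall. That stands as a possibility: with full capture the risk ratio in the illustration is 1.0. Earlier dating in group B would still remain in a time-to-event analysis.

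Finally, Table 1 has no post-baseline row for retinopathy or laser, and its medical history row is marked only at baseline. A separate common field therefore cannot be taken for granted, and the fix must allow for its absence.

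**Conclusion.** The point holds as a wrong source statement combined with unequal ascertainment. Taken literally, the SAP yields no low-risk events for outcome B. Taken with the obvious substitute, it compares different forms with up to 19 against up to 5 scheduled recordings (9 against 2 by week 104, before the final visit), with no sensitivity analysis for this outcome.

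The size of any bias cannot be derived from the documents. The risk ratios above show sensitivity to assumed capture and are not estimates.

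The scope is one secondary outcome in one comparison. The primary endpoint is unaffected. So is active versus placebo, because both arms are in group B with the same recording. The change is worth making before analysis because otherwise the choice of source is left to the analyst.

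**What to change.** In the SAP, for the high- versus low-risk comparison only:

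1. Define outcome B from the information described for both groups, namely retinopathy status by history and laser treatment, counted as new or worsened since baseline. Name the eCRF field.
2. If no separate post-baseline field exists, use adverse events in group B and significant medical events in group A, mapped to one list of terms. State as a limitation that capture may still differ between the forms.
3. In either case, carry group B events forward to the next annual visit, or to the final visit if none follows, as SAP 6.3.1.3 does for the primary endpoint. This aligns the dates. It does not by itself equalise how often patients were asked.
4. Keep adverse events as the source for active versus placebo.

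The cost is SAP wording, a check of the eCRF, some extra coding if the two forms must be mapped, and coarser event dates in group B.
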